### 7.3. Derived Variable Definitions

#### 7.3.1. Treatment -Emergent Adverse Events

Treatment-emergent adverse events are defined as AEs with an onset date on or after the date of the first dose of study treatment. An AE is a TEAE if it occurs up to 30 days after the last dose of study intervention. TEAEs can be pre-treatment AEs that worsen in CTCAE grade after the start of study treatment.

#### 7.3.2. Creatinine Clearance (CrCL)

The creatinine clearance will be calculated using Cockcroft-Gault formula (1976), defined as:

$$CrCL(ml/min) = \frac{(140 - \text{age (in years)}) \times \text{weight (in kg)}}{72 \times \text{serum creatinine (in mg/dL)}}$$

for males and

$$CrCL(ml/min) = \frac{(140 - \text{age (in years)}) \times \text{weight (in kg)}}{72 \times \text{serum creatinine (in mg/dL)}} \times 0.85$$

for females. Baseline weight will be used.

### 7.4. Handling of Missing and Partial Data

#### 7.4.1. Missing Data

Missing data occurs when any requested data is not provided, leading to blank fields on the collection instrument. These data will be indicated using a “blank” in participant listing displays. Note that if any non-date missing data is imputed, the imputed data will only be used in summaries and will not be included in any listing. Answers such as “Not applicable” and “Not evaluable” are not considered to be missing data and will not be displayed as missing.

Imputed dates will not be used to derive study day or duration. Imputed dates will be displayed in listings and identified as imputed.

#### 7.4.2. Imputation of Non-date Missing Data

Data used for evaluating efficacy and safety endpoints may be missing for technical reasons (e.g., unreadable scan, participant missed appointment).

The primary efficacy analysis for ORR will be performed on the Efficacy-evaluable analysis set.

Jazz Pharmaceuticals, Inc.

JZP712-201 Statistical Analysis Plan - Protocol Amendment

2

For participants without any post baseline disease assessment, the response will be imputed as non-responder for sensitivity analyses of ORR in the Safety analysis set.

AEs and SAEs with missing relationship to study treatment will be considered related to study treatment for the purpose of analyses.

AEs and SAEs with missing severity (CTCAE grade) will be considered missing for the purpose of analyses.

#### 7.4.3. Incomplete and Missing AE Start Date

The following imputation rules will be followed, when the AE start date is incomplete (e.g., only *year* is present, but *month* and *day* are missing) or completely missing:

- If *year* is missing (including the situation where the start date is completely missing), set the date to the first dose date.
- If *year* is present, and *month* and *day* are missing, or *year* and *day* are present, and *month* is missing,
  - if *year* = year of first dose, set the date to the first dose date,
  - if *year* < year of first dose, set *month* and *day* to December 31st.
  - if *year* > year of first dose, set *month* and *day* to January 1st.
- If *year* and *month* are present, and *day* is missing,
  - if *year* = year of first dose, and
    - if *month* = month of first dose, set *day* to day of first dose;
    - if *month* < month of first dose, set *day* to the last day of *month*;
    - if *month* > month of first dose, set *day* to the first day of *month*;
  - if *year* < year of first dose, set *day* to the last day of *month*;
  - if *year* > year of first dose, set *day* to the first day of *month*.
- For all other cases that are not covered above, set the date to the first dose date.

Imputed dates for AEs with partial dates will be used to identify treatment emergent AEs and for sorting in data listings. They will not be used to calculate duration of AEs. If an AE start or end date is completely missing, then the duration of the AE will be set to missing and the AE will be considered treatment emergent.

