8.4.1. Time Period and Frequency for Collecting AE and SAE Information

All AEs and SAEs will be collected from the start of intervention until the EOT or E/D visit as specified in the SoA (Table 3) and per Section 8.4.3. Participants' discontinuation from study treatment with an ongoing treatment-related AE should be followed until satisfactory resolution per the investigator. Any spontaneous reporting of treatment-related SAE during the OS follow-up will be also collected and reported.

Note: All SAEs that occur after the consent form is signed but before study intervention/treatment must be reported by the investigator if they cause the participant to be

excluded from the trial, or are the result of a protocol-specified intervention, including but not limited to diet, placebo treatment, or a procedure.

Medical occurrences that begin before the start of study intervention but after obtaining informed consent will be recorded as Medical History/Current Medical Conditions, not as AEs.

All SAEs will be recorded and reported to the sponsor or designee immediately and within 24 hours of first knowledge of the event by study personnel, as indicated in [Appendix 4](#). The investigator will submit any updated SAE data to the sponsor within 24 hours of it being available. All treatment-related deaths will be reported as SAEs. Deaths due to progression of disease are not SAEs and should not be reported as SAEs.

Investigators are not obligated to actively seek information on new AEs or SAEs after conclusion of the study participation. However, if the investigator learns of any SAE, including a death, at any time after a participant has been discharged from the study, and he/she considers the event to be reasonably related to the study intervention or study participation, the investigator should promptly notify the sponsor.

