9.4.1.3.2. Imputation of Partial Dates

Imputed dates will not be used to derive study day or duration. In addition, imputed dates are not used for deriving the last contact date for OS. Imputed dates will be displayed in listings and identified as imputed.

AEs with partial dates will have imputed dates used to identify treatment emergent AEs and for sorting in data listings. They will not be used to calculate duration of AEs. If an AE start or end date is completely missing, then the duration of the AE will be set to missing.

Algorithms for imputing partial dates will be provided in the SAP.

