### 10.2.1. Treatment Emergent Adverse Events (TEAEs)

Treatment-emergent adverse events (TEAE) are defined as AEs with an onset date on or after the date of the first dose of the study treatment and within 30 days of last dose received (the 30-day safety window). TEAEs can be pre-treatment AEs that worsen in CTCAE grade after the start of study treatment. For the purpose of determining treatment-emergent, incomplete and missing AE start dates will be imputed as specified in [Section 7.4.3](#).

Treatment-related AEs are those for which investigators answer “Yes” to the question “Is this adverse event related to study treatment [lurbinectedin]?” in the CRF. Events for which investigators do not record the relationship to lurbinectedin will be considered as related to lurbinectedin for summary purposes. By-participant listings for those events for which the investigator does not record relationship to lurbinectedin will show treatment relationship as missing.

The severity of AEs will be recorded using the Common Terminology Criteria for Adverse Events (CTCAE), version 5.0. Adverse events are graded by the investigator as Grade 1 (mild), Grade 2 (moderate), Grade 3 (severe), Grade 4 (life threatening), or Grade 5 (fatal). The severity grade of events for which the severity was not recorded will be categorized as “missing” for summaries and listings and will be considered the least severe for the purposes of sorting for data presentation.

The following summaries of TEAEs (number and percentage of participants) will be provided overall (across all cohorts) using Safety analysis set:

Jazz Pharmaceuticals, Inc.

JZP712-201 Statistical Analysis Plan - Protocol Amendment

2

- Summary of any TEAEs by worst CTCAE grade (any grade, grade 3-4, grade 5) presented by SOC/PT
- Summary of TEAEs by PT (decreasing frequency)
  - Any grade
  - Grade 3-4
  - $\geq$  Grade 3
- Summary of any non-serious TEAEs by worst CTCAE grade (any grade, grade 3-4, grade 5) presented by SOC/PT
- Summary of treatment-related TEAEs by worst CTCAE grade (any grade, grade 3-4, grade 5) presented by SOC/PT
- Summary of treatment-related TEAEs by PT (decreasing frequency)

A by-participant TEAE listing will be provided with participant identifier, cohort, SOC, PT, start date, end date, severity grade, seriousness, relationship to lurbinectedin, and outcome of the AE using Safety analysis set.

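### SAP 7.4.3 makes an AE treatment emergent when only its end date is missing, even if its known onset lies outside the window that defines a TEAE

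*SAP*

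**What the plan says.** **Definition.** SAP 7.3.1 sets the lower bound: "Treatment-emergent adverse events are defined as AEs with an onset date on or after the date of the first dose of study treatment". It then sets the upper bound: "An AE is a TEAE if it occurs up to 30 days after the last dose of study intervention". SAP 10.2.1 restates both as onset "on or after the date of the first dose of the study treatment and within 30 days of last dose received". Both sections also admit pre-treatment AEs that worsen in grade. The end date plays no part.

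**Missing dates.** SAP 7.4.3, which is headed as a section on AE start dates, gives imputation rules for the start date and closes with a sentence that applies when either the start or the end date is wholly absent: "then the duration of the AE will be set to missing and the AE will be considered treatment emergent". It sets no condition that the onset be unknown.

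**Protocol.** Section 9.4.1.3.2 has the matching sentence and stops at the duration: "If an AE start or end date is completely missing, then the duration of the AE will be set to missing".

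**Collection.** Protocol 8.4.1 collects AEs up to the EOT or early-discontinuation visit, and adds: "Any spontaneous reporting of treatment-related SAE during the OS follow-up will be also collected and reported". The same section requires certain SAEs between consent and first dose to be reported.

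**The concern.** The SAP gives two rules for one flag, and they can return different answers for the same event. Under 7.3.1 and 10.2.1 an AE that began 31 days after last dose is not a TEAE. Under the last sentence of 7.4.3 it is one if its end date is blank and is not one if the end date was recorded. Whether an event is counted would then depend on how complete its record is, not on when it began.

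An AE still ongoing at the data cutoff normally has no end date. SAP 7.4.5 deals with this for medications by exempting items marked as ongoing. SAP 7.4.3 has no equivalent for AEs, so a programmer following the text could flag every ongoing AE, whatever its onset. Safety is a secondary objective, and the TEAE flag feeds the main AE tables.

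**Working it through.** There is no figure in the plan to reproduce. The check applies the two rules to the same events.

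**Rules.** Let F be the first dose date and L the last dose date.

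- Rule A (SAP 7.3.1, 10.2.1): TEAE if F ≤ onset ≤ L + 30 days.
- Rule B (SAP 7.4.3, last sentence, read literally): TEAE if the start or end date is completely missing; otherwise Rule A.

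**Assumed example.** First dose on day 1 and last dose on day 64 (four cycles at 3-week intervals: days 1, 22, 43, 64). The window then closes on day 64 + 30 = 94. The latest in-window EOT visit is at L + 30 + 7 = L + 37 (protocol 7.1), which is day 101. The onset at L + 120 is an arbitrary date in OS follow-up. All onsets are fully known, and none of the AEs is a pre-treatment AE that worsened.

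| AE | Onset day | End date | Rule A | Rule B |
|---|---|---|---|---|
| Pre-dose SAE | −5 | missing | No | **Yes** |
| On treatment | 40 | missing | Yes | Yes |
| L + 30 | 94 | missing | Yes | Yes |
| L + 31 | 95 | missing | No | **Yes** |
| L + 37 | 101 | missing | No | **Yes** |
| Related SAE, L + 120 | 184 | missing | No | **Yes** |
| L + 31 | 95 | day 104 | No | No |
| L + 120 | 184 | day 194 | No | No |

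The rules conflict in four rows, all with an out-of-window onset and a missing end date. For the L + 31 and L + 120 onsets, recording an end date removes the conflict. In-window events are TEAEs under both rules.

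**What the clause adds.** The first bullet of 7.4.3 already sets a completely missing start date to the first dose date, which satisfies Rule A. For missing start dates the clause therefore changes nothing. It alters status only through a missing end date.

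**Whether such events reach the tables.** Days 31 to 37 can be collected when the EOT visit is late, and related SAEs can arrive throughout OS follow-up. The AE tables use the Safety analysis set, so a pre-dose SAE matters only if the participant was later dosed.

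**Which tables.** SAP 10.2.2 to 10.2.4 limit the SAE, discontinuation and dose-modification analyses to the period from first dose to the end of the 30-day window. The TEAE tables in 10.2.1 and the overview in 10.2.7 repeat no such limit and rely on the TEAE flag. The overview includes a row for serious treatment-related TEAEs. A late, ongoing, related SAE could be counted in that row and be absent from the treatment-related SAE table in 10.2.2.

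**Size.** SAP 10.2 plans the AE tables across all cohorts. One participant is 1/60 = 1.7 percentage points at the initial 60, and 1/300 = 0.3 points at about 300. This is the most one participant can move a row. Participants are counted once per row, so a late event changes a count only if that participant has no in-window event in the row, or if it raises the worst grade.

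**The case against.** The strongest defence is that the sentence is loose but its intent is clear. It closes a section on start dates, and 10.2.1 refers to 7.4.3 only for incomplete and missing start dates. SAP 7.4.1 describes missing data as requested data that were not supplied, and says that answers of not applicable do not count as missing. On that view the end date of an ongoing AE is not applicable, and the clause reaches only resolved AEs with a blank end date, which a data query could settle. This shows the likely intent. It does not secure it: 7.4.5 spells out the ongoing exception for medications and 7.4.3 omits it for AEs, while the operative sentence names the end date outright.

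Two further points of the defence stand in full. Going beyond the protocol is not an error in itself, because protocol 9.4.1.3.2 leaves the imputation algorithms to the SAP. The fault is the conflict with the SAP's own definition. In addition, the date limits in 10.2.2 to 10.2.4 protect the tables they govern.

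A reader might infer more than the documents support:

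- *That the treatment-related SAE tables would change.* They are bounded by date in 10.2.2, whatever the flag says.
- *That one participant moves a rate by 5 points, as 1/20.* SAP 7.1 does speak of safety analyses by cohort as well as across cohorts, but 10.2, 10.2.1 and 10.2.7, which govern the AE tables, plan them across cohorts.
- *That late SAEs are usually unresolved.* Nothing says so. Protocol 8.4.3 requires SAEs to be followed to resolution, stabilization, another explanation or loss to follow-up.

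**Conclusion.** The point holds as an internal contradiction in the SAP. As written, the last sentence of 7.4.3 misclassifies AEs that have a known out-of-window onset and a completely missing end date. A partial end date does not trigger it. The exposure is confined to the TEAE tables in 10.2.1 and the overview in 10.2.7, with possible disagreement between the overview and 10.2.2.

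The effect is small. The number of events cannot be derived from the documents and is probably low, and each affected participant moves a pooled row by at most about 1.7 points of 60. The ORR analysis and the futility rules are untouched. The conclusion rests on a literal reading. How far it extends to ongoing AEs depends on whether their blank end dates are treated as missing, which the SAP does not settle.

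**What to change.** Split the last sentence of SAP 7.4.3 into two rules:

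1. If the AE start date or the AE end date is completely missing, the duration is missing.
2. If the AE start date is completely missing, the AE is treatment emergent. An AE with a known onset follows 7.3.1 and 10.2.1 whatever its end date, including when it is ongoing.

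This removes all four conflicts in the table above and leaves in-window AEs as TEAEs by onset. Simply striking the reference to the end date would not do, because that would also drop the duration rule for missing end dates, which protocol 9.4.1.3.2 requires.

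The cost is an edit to one sentence and the matching program specification, made before database lock. It needs no new data and no protocol amendment.

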#### 7.4.4. Incomplete and Missing Prior and Concomitant Medication Start Date

The following imputation rules will be followed, when the prior and concomitant medication start date is incomplete (e.g., only *year* is present, but *month* and *day* are missing) or completely missing:

- If *year* is missing (including the situation where the start date is completely missing), do not impute, and the start date will be treated as missing in the analysis. Medications with missing start date will be considered concomitant for the purpose of summary tables.

Jazz Pharmaceuticals, Inc.

JZP712-201 Statistical Analysis Plan - Protocol Amendment

2

- If *year* is present, and *month* and *day* are missing, set *month* and *day* to January 1st.
- If *year* and *month* are present, and *day* is missing, set *day* to the first day of *month*.
- If *year* and *day* are present, and *month* is missing, set *month* to January.

#### **7.4.5. Incomplete and Missing Prior and Concomitant Medication End Date**

The following imputation rules will be followed, when the prior and concomitant medication end date is incomplete (e.g., only *year* is present, but *month* and *day* are missing) or completely missing:

- If it is indicated that the medication is ongoing (i.e., “Yes” is checked for the question “Ongoing?” in the CRF), do not impute, since there should not be an end date for this medication.
- If *year* is missing (including the situation where the end date is completely missing), do not impute, and the end date will be treated as missing in the analysis.
- If *year* is present, and *month* and *day* are missing, set *month* and *day* to December 31st.
- If *year* and *month* are present, and *day* is missing, set *day* to the last day of *month*.
- If *year* and *day* are present, and *month* is missing, set *month* to December.

#### **7.5. Hypotheses Testing**

This nonrandomized multi-cohort signal finding study will use estimation rather than hypothesis testing to characterize the ORR for each cohort.

#### **7.6. Level of Significance & Multiplicity Adjustment**

Not applicable.

#### **7.7. Subgroups and Subgroup Analyses**

No subgroups and subgroup analyses are planned. However, the influence of baseline and demographic characteristics on the treatment effect may be explored via exploratory subgroup analyses if the number of subjects in the subgroup category is  $\geq 5$ .

#### **7.8. Changes to Planned Analyses**

None.

### **8. STUDY POPULATION SUMMARIES**

#### **8.1. Enrollment**

All participants who signed informed consent will be accounted in this study (Enrolled analysis set).

Jazz Pharmaceuticals, Inc.

JZP712-201 Statistical Analysis Plan - Protocol Amendment

2

The number of participants screened, number of screen failures and reasons for screen failure (did not meet eligibility criteria, withdrew consent, adverse event, investigator discretion, lost to follow-up, study enrollment closed, other) will be summarized overall and by assigned cohort (as per IRT) and details will be included in a data listing using Enrolled analysis set.

The number and percentage of participants included in each analysis set (Safety, Efficacy Evaluable, [REDACTED] and reason(s) for exclusion from each analysis set will be summarized by assigned cohort: UC, PD-NEC, HRD-positive tumor agnostic malignancies. Percentages for Safety analysis set will be based on number of enrolled participants in each cohort. Percentages for Efficacy Evaluable [REDACTED] analysis sets will be based on number of participants in each assigned cohort in Safety analysis set.

## 8.2. Disposition

Participant disposition will be summarized (number and percentage) overall and by assigned cohort for Enrolled analysis set. Participant disposition data, including study treatment completion, study treatment discontinuation, study completion, study withdrawal, primary reason for study treatment discontinuation, and primary reason for study withdrawal as provided on the CRF, will be listed by participant for Enrolled analysis set. Study treatment completion and study completion status will be assessed based on corresponding CRF pages. The number and percentage of participants followed-up for survival status will be summarized by assigned cohort and listed for Safety analysis set.

If a participant completes the study per protocol, the last on-study date is the last visit date for this participant; if a participant terminates the study early, the date entered in the early termination folder in eCRF is the last on-study date for this participant.

## 8.3. Protocol Deviations

Protocol deviations will be categorized as important and non-important. Important protocol deviations will be summarized descriptively for participants with at least one important protocol deviation by cohort. The summary will include the following subtypes:

- Inclusion criteria not met
- Exclusion criteria not met
- Expired/compromised IP administered
- Subject dose not modified per protocol
- Incorrect dose of study treatment
- Failure to take action in response to apparent toxicity and failure to appropriately monitor the patient with toxicity
- Missed pregnancy test
- Failure to complete any efficacy assessments (e.g., imaging evaluations) at any timepoint

Jazz Pharmaceuticals, Inc.

JZP712-201 Statistical Analysis Plan - Protocol Amendment

2

- Failure to obtain initial informed consent, or obtaining informed consent after initiation of study procedures
- Use of an invalid/outdated consent form
- Prohibited medication taken or prohibited treatment given
- Falsification of source documentation
- Significant PI or staff misconduct or fraud
- Breach of confidentiality of participant/data privacy
- IRB approval lapse
- Non-compliance with protocol withdrawal criteria
- Significant, repeated protocol non-compliance that significantly impacts participant safety and/or the integrity of the study conduct or study data

Every subtype will be kept in the summary even if it has 0 participants. A participant with more than one important protocol deviation will be counted only once in the total number of participants with at least one important protocol deviations. A by-participant listing of all protocol deviations will be provided with deviation subtype, description, and a flag for important protocol deviation.

#### **8.4. Demographic and Baseline Characteristics**

Demographic data and other baseline characteristics will be summarized using descriptive statistics overall (across all cohorts) and by assigned cohort for the Safety analysis set and Efficacy evaluable analysis set. The denominator for percentages will be the number of participants in each cohort with non-missing data available for the variable of interest. All demographic data and other baseline characteristics will be included in by-participant data listings using Safety analysis set.

The following demographic and baseline disease characteristics will be included in the summaries mentioned above:

- Age (years) at informed consent (as continuous variable)
- Age group at informed consent: <65 years,  $\geq$  65 years
- Sex at birth (male, female)
- Childbearing potential (female participants only) (yes/no)
- Race (American Indian or Alaska Native, Asian, Black or African American, Native Hawaiian or Other Pacific Islander, White, Multiple, Other, or Not Reported)
- Ethnicity (Hispanic or Latino, Not Hispanic or Latino, or Not Reported)
- Weight at baseline (kg)
- Height at baseline (cm)
- Body surface area (BSA) ( $\text{m}^2$ )

Jazz Pharmaceuticals, Inc.

JZP712-201 Statistical Analysis Plan - Protocol Amendment

2

- Alcohol use
- Tobacco use
- Baseline creatinine clearance (CrCL)
- Baseline ECOG performance status (0, 1)

Baseline results for biochemistry, hematology, coagulation laboratory tests, urinalysis, vital signs, and ECG test results will be reported in the corresponding summary tables and listings for each safety endpoint.

